3.2 Secondary objectives and secondary endpoints

The purpose of the clinical trial is to secondarily investigate whether albumin administration and the maintenance of serum albumin concentrations of at least 30 g/l for 28 days after the onset of septic shock will influence 28- and 60-day mortality, ICU and hospital mortality rates, organ dysfunction/failure as assessed by the SOFA score, ICU and hospital lengths of stay, as well as ventilator- and vasopressor-free days. A cost-benefit analysis of the volume replacement therapy for the ICU stay up to a maximum of day 28 is another objective of this clinical trial.

Secondary end-points therefore are

- 28- and 60-day mortality,
- ICU and hospital mortality,
- organ dysfunction/failure as assessed by the SOFA-Score: recorded daily up to 28 days in the ICU after randomisation in the study,
- ICU and hospital lengths of stay.
- ventilator- and vasopressor-free days,
- cost-benefit of volume replacement therapy: collection of data on the use of human albumin and other colloids and crystalloids,
- · Total amount of fluid administration and total fluid balance, and
- safety-related parameters: occurrence of AEs and SAEs, especially anaphylactic shock, hypervolaemia, and pulmonary oedema.

4. Trial design

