If hypervolaemia is suspected, the trial drug should be administered over a longer period of time (up to 2x the prescribed duration) under close observation of the appropriate haemodynamic parameters. If the association between the trial drug and hypervolaemia is confirmed, an increase in the severity of hypervolaemia is observed, or life-threatening consequences such as pulmonary oedema occur, administration of the trial drug for that day should be stopped. A new clinical evaluation and, if necessary, continuation of the trial drug should take place on the following day.

The SpB must be informed about the permanent termination of the trial drug (discontinuation of treatment). The patient, guardian or legal representative will be informed about discontinuation of treatment for medical reasons as well as the follow-up procedure.

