8.2 Adverse events

According to GCP-V § 3 (30), an Adverse Event (AE) is any unfavourable event that occurs to a patient participating in a clinical trial who has received an investigational medicinal product and that is not necessarily causally related to the treatment. According to ICH-GCP (29), these may be symptoms (including, for example, abnormal laboratory values), diseases or signs that are associated with the use of an investigational medicinal product. This is independent of whether the event is causally related to the investigational product or not. For the ARISS study, assessment of adverse events will also be done in patients of the control group without albumin.

Septic shock, which is the basic inclusion criterion of this clinical trial in all study patients, is one of the most life-threatening clinical pictures. The ICU mortality from severe sepsis and septic shock is 47% according to the prevalence study of the sepsis competence network (7). Many of the patients need mechanical ventilation and about half the patients have acute kidney failure. Hepatic and metabolic parameters are almost always altered depending on the severity of sepsis. Previous studies investigating severe sepsis or septic shock, such as MAXSEP (EudraCT 2006-006984-21) and SISPCT (EudraCT 2007-004333-42), have therefore performed selective AE evaluation that has been shown to be reliable and which should also be used in the ARISS study.

Because most septic patients have altered laboratory values and symptoms because of the underlying disease and are constantly evolving as the disease progresses, the definition of AE is restricted as follows in this clinical trial:

An adverse event in the ARISS is any adverse event that occurs to a study subject that is not necessarily causally related to the trial drug. If an adverse event can be explained by the underlying sepsis, the following applies:

Events plausibly explainable by sepsis are recorded in both groups as sepsis-related clinical events in the daily eCRF visits, but not as AEs. This rule concerns the following clinical events:

- Death caused by severe sepsis or septic shock
- Cardiovascular event requiring the administration of vasoactive substances
- Respiratory event: e.g., decrease in PaO2/FiO2 ratio, hypoxia, ARDS, acute pulmonary dysfunction, and mechanical ventilation
- Hepatic event: e.g., Liver failure or liver dysfunction
- Renal event: e.g., Kidney failure, renal insufficiency

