- Haematological event: e.g., coagulopathy, DIC, thrombocytopaenia, thrombocytosis
- Neurological event: e.g., delirium, confusion

Each sepsis-related clinical event must be documented in the eCRF during the respective visit with specific parameters. The investigator assesses the sepsis-related clinical event in ZKSJ0112 ARISS

Zentrum für Klinische Studien

terms of an association with the trial drug and classifies it as "possible" or "not possible". Documentation of the sepsis-related clinical event as an AE occurs only if the examiner suspects a connection with the administration of the trial drug, which is therefore only possible in the albumin group.

However, the following effects of the trial drug may be substance-specific and must be documented as AE:

- Flush
- Urticaria
- Fever
- Nausea
- Anaphylactic shock
- Hypervolaemia
- Pulmonary oedema
- Transmission of infection (in addition to sepsis, see corresponding section of the valid information brochure).

Clinically relevant worsening of a pre-existing disease not related to sepsis should be considered and documented as an AE.

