11.2 Randomisation

Randomisation will be stratified according to:

- Serum lactate levels within 24 h before inclusion in the trial: ≤ 8 mmol/l vs. > 8 mmol/l and
- centre

in the treatment groups

- albumin group
- control group without albumin

Albumin administration will be adjusted after the starting dose according to serum albumin concentrations. Therefore, blinding will not be possible.

Group assignment will be determined using a validated electronic tool (PaRANDies) after inclusion of the patient. Randomisation will be based on a randomisation list created in advance with nQuery Advisor 7.0.

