6.8 Safety and Tolerability Analyses

6.8.1 Adverse Events

For sepsis related AEs, frequency analysis with respect to categories cardiovascular / respiratory / hepatic / renal / hematological / neurological, will be presented.

Respective entries of AEs possibly related to study medication in AE data base will be selected and presented separately.

All AEs and serious AEs will be presented by incidence analysis of the pre-specified categories as well as intensity, relationship to study medication, measures with respect to study medication as well as other measures and outcome. Events of category "Other" will be listed.

For infections, frequency analysis over types, grade and origin will be provided. Analysis of daily assessed data will be performed over the following time frames: Screening / 6h after randomization / Day 1 / Day 2-7 / Day 8-28.

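### Hypervolaemia and pulmonary oedema: the wording of Protocol 8.2, open-label assessment and the absence of case criteria allow by-arm AE counts to reflect labelling as well as harm

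*Protocol*

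**What the plan says.** Protocol 3.2 lists among the secondary endpoints "safety-related parameters: occurrence of AEs and SAEs, especially anaphylactic shock, hypervolaemia, and pulmonary oedema". Protocol 11.2 explains that dosing follows the serum albumin level and concludes: "Therefore, blinding will not be possible".

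Protocol 8.2 restricts what counts as an AE. Events that sepsis plausibly explains are recorded in both groups in the daily visits, but not as AEs. One listed class is "Respiratory event: e.g., decrease in PaO2/FiO2 ratio, hypoxia, ARDS, acute pulmonary dysfunction, and mechanical ventilation". Such an event moves to the AE section only if the investigator suspects the trial drug, "which is therefore only possible in the albumin group". The next sentence begins a list of names, including hypervolaemia and pulmonary oedema, with the statement that "the following effects of the trial drug may be substance-specific and must be documented as AE". Earlier in the same section, "assessment of adverse events will also be done in patients of the control group without albumin".

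SAP 6.8.1 states: "All AEs and serious AEs will be presented by incidence analysis of the pre-specified categories". SAP 6.2 has all analyses presented by treatment group.

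**The concern.** Two events singled out as safety endpoints are listed by name only, under a heading that calls them effects of the drug, and are recognised by staff who know the allocation. For pulmonary oedema there is also a competing category. The respiratory sepsis-related class is open-ended and includes hypoxia, a falling PaO2/FiO2 ratio and acute pulmonary dysfunction, and no boundary with pulmonary oedema is drawn. Two patients with the same lung findings could therefore be coded differently according to arm.

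Fluid overload is a harm the protocol itself anticipates. If the by-arm table mixes harm with labelling, an apparent excess may be spurious or a real one may be diluted, and either would carry into the benefit-risk conclusion.

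**Working it through.** The point rests on text. The documents give no expected rate, margin or power for either event, so there is no stated figure to reproduce.

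**1. The text, side by side**

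| Question | What the documents give |
|---|---|
| Are controls assessed for AEs? | Yes (Protocol 8.2) |
| Must the two events be recorded as AEs? | Yes, but introduced as drug effects (Protocol 8.2) |
| Can a sepsis-related event become an AE in a control? | No: that needs suspicion of the trial drug (Protocol 8.2) |
| Are there case criteria for either event? | None in the protocol or SAP. Protocol 6.5 speaks of suspicion and then says "If the association between the trial drug and hypervolaemia is confirmed", without saying how |
| Is there blinded adjudication? | None described. The second assessment in Protocol 8.6.2 covers SAEs only, for seriousness, causality and expectedness |
| Are recording windows equal? | No. Albumin group: to 24 h after the last dose. Controls: to day 28 or ICU discharge (Protocol 8.3) |

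The coding ambiguity concerns mainly pulmonary oedema, because hypervolaemia has no obvious sepsis-related class. The lack of criteria and the unblinded recognition concern both.

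**2. What differential labelling could do (illustration only)**

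Assumptions, none from the documents: true incidence *p* is the same in both arms (5, 10 or 20%); 90% of albumin-arm cases are labelled as AEs (s_a) and 80, 70 or 60% of control cases (s_c); observation is equal. I take n = 831 per arm, the number to be randomised.

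Apparent rate = p × s. Apparent relative risk = s_a / s_c. Chance of a nominally significant excess under albumin ≈ Φ(difference / SE − 1.96), with SE = √{[p_a(1 − p_a) + p_c(1 − p_c)] / n}.

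Worked case, p = 10%, 90% v 70%: the rates are 9.0% and 7.0%. SE = √[(0.0819 + 0.0651) / 831] = 0.0133. Then 0.02 / 0.0133 = 1.50, and Φ(1.50 − 1.96) = 0.32.

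| Control labelling | Apparent RR | p = 5% | p = 10% | p = 20% |
|---|---|---|---|---|
| 90% (equal) | 1.00 | 2.5% | 2.5% | 2.5% |
| 80% | 1.12 | 7% | 11% | 19% |
| 70% | 1.29 | 18% | 32% | 60% |
| 60% | 1.50 | 36% | 64% | 93% |

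With 706 per arm the p = 10% column becomes 10%, 28% and 57% for control labelling of 80%, 70% and 60%.

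**3. What the unequal window could do**

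Suppose only a share *w* of the albumin-arm cases that would be seen in the control window falls inside the shorter albumin window. The apparent RR becomes w × s_a / s_c. It returns to 1 when w = s_c / s_a, that is 0.8/0.9 = 0.89, 0.7/0.9 = 0.78 or 0.6/0.9 = 0.67. A modest loss from the shorter window would cancel the apparent excess, and a larger one would reverse it. Likewise, if staff label 70% of albumin cases and 90% of control cases, the multiplier is 0.7/0.9 = 0.78, which would hide a true RR of 1.29.

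**The case against.** A fair reading of 8.2 is that its list is an exception to the sepsis rule. It opens with a contrastive word, makes documentation mandatory, and hedges that the effects may be substance-specific. The section defines an AE without requiring causality and extends assessment to controls. On that reading, coding a control's pulmonary oedema only as a sepsis-related event breaches the protocol. This stands as the probable intention. It does not settle the literal text, which names drug effects immediately after a route closed to controls. Nor does a duty to record define a case.

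Four stronger inferences are tempting, and the documents do not support them.

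- *That AEs are collected only under albumin.* Protocol 8.2 says otherwise.
- *That Protocol 6.5 directs staff to look for hypervolaemia only in the albumin arm.* That section governs handling of the trial drug, so it can concern only patients receiving it. It is not a rule for finding events.
- *That labelling and harm cannot be separated at all.* Sepsis-related respiratory events, fluid balance, SOFA subscores, blood gases and ventilation are also reported by arm, and a reader can set the AE counts against them.
- *That a false excess of some stated size is to be expected.* The rates above are assumed. AE analysis is by frequency tables; a p-value would arise only through the general provision for exploratory tests of secondary endpoints in Protocol 11.3.2.

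The study manual, SAE manual and eCRF are not available here and may contain definitions. The absence is established only for the protocol and SAP.

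**Conclusion.** The point holds in limited form. Wording that can be read as arm-dependent, together with unblinded recognition and no case criteria in the protocol or SAP, means the by-arm incidence of hypervolaemia and pulmonary oedema can reflect differential labelling. Neither the size nor the direction can be derived from the documents. The illustrative relative risks of 1.12 to 1.50 depend wholly on the assumed labelling rates and on equal observation, and the shorter albumin-arm window could work against them. The primary endpoint, all-cause mortality at 90 days, is unaffected. The matter is worth correcting because it touches harms that the protocol itself singles out and because the correction is small.

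**What to change.** 1. **Protocol 8.2.** State that hypervolaemia and pulmonary oedema must be documented as AEs in both groups, whatever the suspected cause and also when sepsis could explain them. Limit this to those two events: applied to the whole list it would bring in fever and similar findings that are part of sepsis. If case criteria exist in the study manual or eCRF, cite them.

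2. **SAP 6.8.1.** Label the investigator-reported counts of these two events as unblinded. Show them by randomised arm beside measures collected in both arms over the same ICU days (Protocol 7.5): 24-h fluid balance, SOFA respiratory subscore, diuretic use and ventilation. Naming the randomised arm matters because SAP 2.3 analyses safety as treated, whereas Protocol 11.3.1 places it in the ITT group. Before reusing fluid balance, check the minus sign before other fluid loss in output definition [2] of SAP 5.3.

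3. **Optional.** Add a programme-derived fluid-overload event as a supportive analysis, with its rule fixed before database lock and without sight of allocation. It would be a non-specific proxy with a partly arbitrary cut. It would also not be fully free of unblinded decisions, since diuretics and ventilation are chosen by staff who know the arm.

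Cost: item 1 is a sentence, but it may need approval as an amendment and has to be communicated to 40 to 50 centres. Items 2 and 3 are SAP changes; item 2 needs no new data, and item 3 needs none if its rule uses only recorded items. If the protocol is not reopened, item 2 can be done alone, with the ambiguity stated beside the table.

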8.3 Duration of recording adverse events

Recording of AEs and sepsis-related adverse events begins at randomisation. Because the study drug is human albumin, which is a normal constituent of human blood plasma, and does not differ in its effects from physiologic albumin, recording and follow-up of AEs and SAEs for a maximum of 24 hours after the last dose of the trial drug is considered to be sufficient. Therefore, AEs and sepsis-related adverse events will be recorded

- in the albumin group until 24 h after the last dose of the trial drug and
- in the control group without albumin until day 28 after randomisation or until discharge from the ICU, if it occurs before day 28 after randomisation.

In the event that AEs or SAEs are still "ongoing" after the above dates, they will be tracked until maximum the end of data collection (Day 90). If they are "ongoing" on day 90, they are documented as "not recovered," "recovered with sequelae," or "unknown."

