6.5 Discontinuation of the trial interventions- discontinuation due to a medical reason

The decision to discontinue or to continue treatment with the trial drug from a medical point of view will be at the discretion of the treating physicians (members of the trial group).

Premature discontinuation of treatment with the trial drug does not lead to termination of the study. Further observation and documentation will be continued.

Human albumin is a normal component of human plasma and does not differ in its effects from physiological albumin. According to the current drug information brochure, toxicity tests for single-use human albumin in animals are of little relevance and do not enable determination of the toxic or lethal dose or a dose-response relation. The target serum albumin concentration in the clinical trial is within the normal range of human plasma albumin (mindestens 30 g/l), so that overdose is unlikely.

According to the current drug information brochure, the following adverse effects may occur with Albutein® 200 g/l or Plasbumin® 20:

- Mild reactions, such as flush, urticaria, fever, and nausea, are rare.
- In very rare cases, anaphylactic shock can occur.
- The possibility of transmitting an infection cannot be completely ruled out despite standard measures of preventing infections caused by drugs made from human blood or plasma. This also applies to all unknown or newly emerging viruses or other pathogens.

MIId reactions, such as flush, urticaria, fever and nausea, usually disappear quickly when the infusion rate is reduced or the infusion is stopped.

If such reactions occur, appropriate therapy should be initiated if clinically indicated. This includes therapy with antihistamines and symptomatic therapy.

In these cases, the trial drug should be subsequently administered over a longer period of time (up to twice the prescribed duration), with close monitoring of the relevant clinical

parameters. A new clinical evaluation and, if necessary, treatment with the trial drug should continue on the following day. If the reaction reoccurs, the trial preparation will be permanently stopped.

If anaphylactic shock occurs, infusion of the trial drug should be discontinued and adequate treatment should be initiated according to current recommendations for treating shock. Administration of the trial drug will be permanently stopped.

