7.5.2 Data collection at trial days 28, 60, and 90 after randomisation

At these time points, data will be collected on the primary and secondary "mortality" outcomes. If the patient has already left the hospital before these time points, contact with the patient, his quardian or legal representative will take place to collect the required data.

- Vital status (alive/dead): if applicable date of death and cause of death; if applicable, recording of "end of life" decisions, stay after discharge
- · Verification of the documentation of SAEs already detected and serious sepsis-related clinical events, possibly AEs, which are "ongoing" at the respective time point

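### Recording of new AEs stops 24 hours after the last albumin dose, so the trial cannot support a conclusion on delayed transmission of infection, a mandatory AE term

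*Protocol*

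**What the plan says.** **The risk.** Protocol 6.5, on the adverse effects of the product: "The possibility of transmitting an infection cannot be completely ruled out despite standard measures". It adds: "This also applies to all unknown or newly emerging viruses or other pathogens".

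**The duty to record.** Protocol 8.2 lists effects that may be specific to the substance and have to be entered as AEs. One of them is: "Transmission of infection (in addition to sepsis, see corresponding section of the valid information brochure".

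**The window.** Protocol 8.3 starts recording at randomisation and considers that observation "for a maximum of 24 hours after the last dose of the trial drug is considered to be sufficient". The reason given is that albumin is a normal plasma constituent whose effects match those of physiological albumin. New events are entered "in the albumin group until 24 h after the last dose of the trial drug". For controls, the window closes at day 28 or at ICU discharge, whichever comes first. Only events still ongoing at those dates are tracked to day 90; footnote 10 of the visit schedule (1.6) says the same.

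**Later contacts.** At hospital discharge (7.5.1), data are taken on ongoing SAEs and serious sepsis-related events. At days 28, 60 and 90 (7.5.2) the task is "Verification of the documentation of SAEs already detected", together with events still ongoing. Protocol 6.8 says no specific follow-up is needed once dosing has ended.

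**Infection data outside the AE form.** Protocol 7.5 collects infection, microbiology and anti-infective data on study days 1 to 28, in both arms, while the patient is in the ICU. This is not tied to the last dose. SAP 6.8.1 tabulates infections by type, grade and origin, and SAP 6.8.2 tabulates pathogens by source.

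**Traceability.** Protocol 6.1 requires product name and batch number for each treatment with the trial drug.

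**The concern.** The 24-hour limit rests on what albumin does in the body. The risk named in 6.5 concerns what a plasma product might carry, and nothing in 8.3 explains why 24 hours would be enough for that. If a transmitted infection is first recognised after the window has closed and the patient has left the ICU, no planned contact asks about it.

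At stake is the meaning of a safety statement. With transmission of infection as a named AE term, a safety table could show a count of zero. A reader could take that as evidence against transmission at any time, although the recording rules cover only part of the period in which a case could appear. The batch link is kept, but no question is asked after the window that would make use of it.

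**Working it through.** The plan states no figure on this point, so there is none to reproduce. The check compares the recording routes, then shows how much a zero count depends on the unknown latency.

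**Step 1. Which cases have a route?**

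| When the infection is first recognised | Route in the plan |
|---|---|
| During dosing, or within 24 h of the last dose | AE/SAE recording (8.2, 8.3) |
| Later, still in the ICU, up to day 28 | Daily infection and microbiology data (7.5; SAP 6.8.1, 6.8.2), not as a new AE |
| Later, after ICU discharge | None: 7.5.1 and 7.5.2 cover only ongoing or already detected events |

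The middle route has limits. Sampling for developing infections is left to the treating physician (section 7, general remarks), the routine laboratory list contains no viral or serological test (1.6; SAP 4.4.2), and the daily-data time frames in the SAP end at day 28.

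**Step 2. Length of the AE window.** For a last dose on day d, recording of new AEs in the albumin arm closes at about day d + 1. The time left to day 90 is 90 − (d + 1).

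| Last dose, day d | Window closes, about day | Days left to day 90 |
|---|---|---|
| 0 (starting dose only) | 1 | 89 |
| 3 | 4 | 86 |
| 7 | 8 | 82 |
| 14 | 15 | 75 |
| 28 (maximum) | 29 | 61 |

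These days apply to AE-form recording in a patient alive at day 90.

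**Step 3. What a zero count can exclude.** Inputs: 831 randomised per arm (synopsis; 1412/0.85 = 1661.2, which gives the planned 1662), or 706 evaluable per arm (Protocol 11, sample size). Let s be the share of true cases that appear and are recognised inside the window. **s is an assumption; the documents give no latency.** With zero recorded cases, the one-sided 95% upper limit for the true risk is [1 − 0.05^(1/n)] / s. For n = 831 and s = 1 this is 1 − 0.05^(1/831) = 0.0036. The last column is the chance of recording no case if the true risk were 0.5% (an illustrative value): (1 − 0.005 × s)^831.

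| s (assumed) | Upper limit, n = 831 | Upper limit, n = 706 | Chance of zero at 0.5% risk, n = 831 |
|---|---|---|---|
| 1 | 0.36% | 0.42% | 0.016 |
| 0.50 | 0.72% | 0.85% | 0.125 |
| 0.25 | 1.4% | 1.7% | 0.35 |
| 0.10 | 3.6% | 4.2% | 0.66 |
| 0.05 | 7.2% | 8.5% | 0.81 |

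The limit weakens in proportion to 1/s. A zero count loses all information only as s approaches 0.

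**The case against.** The strongest case on the other side has four parts.

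- **The window is not negligible.** It opens at randomisation and stays open throughout dosing. A patient dosed to day 28 is observed for about 29 days after first exposure, and ICU infection data continue to day 28 whatever the last dose. A reader might infer that transmission cannot be observed at all and that a zero count would be empty. The documents do not support that. This objection stands.
- **The 61 to 89 days overstate the loss.** They count from the last dose although exposure starts with the first. They ignore deaths, which the planning assumptions put at 50% (control) and 42.5% (albumin) by day 90. They also leave out the ICU infection data. This stands too: the days describe a recording rule, not lost observation.
- **No conclusion on transmission is planned.** The safety endpoint in 3.2 highlights anaphylactic shock, hypervolaemia and pulmonary oedema, and SAP 6.8.1 is descriptive. That is true, and 8.2 and 8.3 do not contradict each other: one names the event, the other limits the time. But the AE term is mandatory and its result can be read, so the limit should be stated.
- **Asking later would not settle the question.** No serology is planned and the trial is open-label, so reports would rest on suspicion, and nearly all would come from the albumin arm. This stands, and rules out a between-arm comparison. It does not remove the value of a route for a case that someone does diagnose.

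**Conclusion.** The point holds in a limited form. The rationale for the 24-hour limit does not cover transmission of infection, and a case first recognised after the window and after ICU discharge has no planned way into AE or SAE recording. A zero count therefore cannot support a conclusion on **delayed** transmission. It still carries information on early-onset cases and on those arising while dosing continues.

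The size cannot be fixed from the documents. Under the assumed range of s from 1 to 0.05, zero in 831 excludes risks above 0.36% to 7.2%. Very few cases are expected, so this is an improvement worth having and does not threaten the primary result or the sample size. The unequal AE windows between arms are a separate matter: a common end at day 28 or ICU discharge would leave this gap open.

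**What to change.** 1. **Protocol 8.3:** exempt suspected transmission of infection from the 24-hour limit.
2. **Protocol 7.5.1 and 7.5.2:** at hospital discharge and at the existing day 28, 60 and 90 contacts, ask about newly diagnosed infections suspected to come from an albumin product. Include non-trial albumin, which 6.6 permits in controls. Record such cases as AE or SAE with the batch number. For the trial drug it is already documented under 6.1; for other albumin, 6.6 asks only that the drug be documented, so the batch may have to be taken from the patient record.
3. **SAP 6.8.1:** list these cases descriptively, without a between-arm comparison.
4. **Study report:** state that no systematic testing was done and that absence of reports does not exclude delayed transmission.

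Cost: one eCRF item, one question at contacts that already take place, and a few extra causality assessments. There are no new visits or tests, and the sample size does not change. Ascertainment will remain incomplete and based on suspicion, which is why item 4 is needed even if items 1 to 3 are adopted.
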